### 3. STUDY DESIGN

#### 3.1 Overview of Study Design

This multicenter phase III clinical study evaluates the efficacy, safety and immunogenicity of a cell-based quadrivalent subunit influenza virus-vaccine (QIVc) compared to non-influenza vaccine in subjects between 6 months through 47 months of age. The study features an observer blind design, parallel groups and 1:1 randomization between QIVc and the non-influenza vaccine. Based on previous influenza vaccination history, subjects will receive either one or two doses of either QIVc or comparator (non-influenza vaccine/placebo). The non-influenza vaccine is a conjugate vaccine for prevention of invasive disease caused by *Neisseria meningitidis* serogroup C (MenC vaccine). In subjects who require two doses, MenC and placebo (saline for injection) will be administered separated by 28 days. In this study placebo will be used as masking dose. All subjects aged 6 through 11 months at enrollment, regardless of treatment assignment, will receive a dose of the MenC vaccine at the end of the study. For the subjects allocated to the immunogenicity sub-set, blood samples will be collected during clinical visits to allow immunogenicity analyses to further characterize the study population for baseline titers, response to vaccination and to understand the observed efficacy. An Interactive Response Technology (IRT) system will be used for subject randomization into the treatment group and into the immunogenicity sub-set.

The study is designed to accrue an approximate number of subjects and a minimum number of cases over several influenza seasons, i.e. both a minimum of 191 RT-PCR confirmed influenza cases and a minimum of 104 culture confirmed influenza cases antigenically matched to the strains selected for the seasonal vaccine. If the overall/pooled influenza attack rate differs from the predicted and/or influenza strain circulation within a study season has drifted or shifted away from the strains selected for the seasonal vaccine, an adjustment of the prospectively specified number of cases, and number of subjects may be required. Extraneous real-life information, from (but not limited to) the influenza surveillance systems of the European Center for Disease Control (ECDC), US Center for Disease Control and Prevention (CDC) or World Health Organization (WHO) may be used to re-assess the influenza event rate.

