### Primary Efficacy Analysis:

Nasopharyngeal swab samples in this study will be analyzed in batches and the number of RT-PCR confirmed influenza cases and its antigenic match to the influenza vaccine strain will be reviewed on a regular basis (blinded review) throughout the study.

An interim analysis for efficacy may be performed, if deemed necessary by the Sponsor:

- If the number of RT-PCR confirmed influenza cases is less or equal to 95 overall, no interim analysis for efficacy will be done and the study will be extended because the probability to make a conclusion for efficacy is too low.
- If the number of RT-PCR confirmed influenza cases is greater or equal to 96 but less than 191, an unblinded interim analysis for efficacy may be performed. To maintain the overall alpha,  $\alpha = 1.25\%$  (1-sided), for the hypotheses testing for the primary objectives, an error-spending-function will be used. The benefit of using an error-spending-function is that no maximum number of analysis stages and the timing of the analyses need to be pre-specified, what in practice means that the duration of the study in terms of number of seasons can be left open. In this case

$\alpha$ -boundaries, forming the adjusted probabilities for the type I error, are calculated using error-spending function and if the p-value for one primary objective is lower than the respective  $\alpha$ -boundary the trial stops early (i.e., without reaching the targeted number of cases of 191) for efficacy. Otherwise, the trial continues enrollment. Decisions to stop or continue the trial will be made on the basis of discussions between the DMC and Senior Management.

- If the number of RT-PCR confirmed influenza cases is greater or equal to 191, the study may be unblinded and the final analysis may be performed by the Sponsor. If the trial proceeds to the final analysis (upon reaching 191 cases) the boundaries for acceptance or rejection are identical to the assumed type I and type II errors for the overall design, and the trial stops to either reject or accept the null hypothesis of either one or / and the other of the primary objectives.

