2.3 Sample Size and Power

This study is planned using a group sequential design, with one or more interim analyses for efficacy using O'Brien-Fleming efficacy bounds. The statistical test performed will depend on the number of RT-PCR confirmed influenza cases and the number of culture confirmed influenza cases, so the sample size estimate is only for operational reasons (an estimate of number of subjects needed to assess the endpoint).

For the primary efficacy endpoint for RT-PCR confirmed illness (1a), assuming an attack rate in the comparator group of 8% and an influenza vaccine efficacy of 40%, an estimated sample size of minimally 2,974 evaluable subjects (or 1,487 evaluable subjects per study group) with a minimum total of 191 cases are needed to have at least 90% power to reject the null hypothesis that the VE is less or equal to 0% at the significance level $\alpha=0.0125$ and the risk of infection contained entirely within period covered by follow-up. For the primary efficacy endpoint for vaccine antigenically matched strains (1b), assuming an attack rate in the comparator groups of 4%, a VE of 50%, $\alpha=0.0125$, a minimum of 3,446 evaluable subjects and a minimum number of 104 cases are needed to have at least 90% power to reject the null hypothesis that the VE is less or equal to 0% at the significance level $\alpha=0.0125$. These results assume that the hazard ratio is constant throughout the study and that Cox proportional hazard regression is used for the analysis. The following table summarises the power calculations assumptions and the number of cases required to meet primary efficacy endpoints.

Statistical Analysis Plan – Final v2.0

Sponsor Name: Seqirus UK Limited
 Sponsor Protocol ID: V130_14

Table 1. Power calculation for Multiple Primary Endpoints

Primary Objective	VE Success Criteria	Assumed VE	Alpha (α)	Influenza attack rate in comparator group	Power	Minimum number evaluable subjects per Treatment Group	Minimum total subjects Enrolled	Minimum number of ILIs to demonstrate LL 97.5% CI for VE is > 0%
1a	0%	40%	0.0125	8%	>90%	1,487	3,306	191
1b	0%	50%	0.0125	4%	>90%	1,723	3,830	104

Accounting for 10% early dropout and uncertainty about the assumed parameters, an approximate number of 3,830 subjects are planned to be enrolled (or 1,915 subjects per study group) to demonstrate that the lower limit (LL) of the two-sided 97.5% CI for the VE is greater than 0% for the primary endpoint assessment.

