The study is designed to accrue a minimum of 191 RT-PCR confirmed influenza cases and a minimum of 104 culture confirmed influenza cases antigenically matched to the strains selected for the seasonal vaccine.

If the overall/pooled influenza attack rate differs from the predicted and/or influenza strain circulation within a study season has drifted or shifted away from the strains selected for the seasonal vaccine, an adjustment of the prospectively specified number of cases, and number of subjects may be required. Extraneous real-life information, from (but not limited to) the influenza surveillance systems of the European Center for Disease Control (ECDC), US Center for Disease Control and Prevention (CDC) or World Health Organization (WHO) may be used to re-assess the influenza event rate.

Sample Size for Secondary Immunogenicity Objectives (Immunogenicity Sub-set):

Per season, with a 1:1 allocation, approximately 100 evaluable subjects from the active arm and 100 evaluable subjects from the comparator arm will be enrolled into the immunogenicity sub-set. Assuming a 10% drop out rate approximately 222 subjects will be allocated to the immunogenicity sub-set per influenza season.

Sample Size for Safety:

With a Safety Population of 1,723 evaluable subjects in the safety set of QIVc, AEs with population rates of 1 in 1,000 have an 82.2% probability of being detected. Events with population rates of 1 in 575 have a 95% chance of being observed with n=1,723. Events with population rates of 1 in 2,000 have a 57.8% chance of being observed with n=1,723.

Sample size calculations were performed using PASS v12.0.2.

3 Efficacy and Safety Variables

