6.8 Interim Analysis

As the circulation of influenza viruses is seasonal and the event rates of influenza are difficult to predict, this study is group sequentially designed to allow for analyses of interim data to enable early study termination when a statistically robust demonstration of efficacy is observed.

An event-driven interim analysis may be performed if deemed necessary by the Sponsor.

In the event an interim is performed, the goal of the interim analysis is to be able to stop the study for early evidence of efficacy. For this analysis a restricted unblinding will be done, i.e. only external Data Monitoring Committee (DMC) members and Contract Research Organization (CRO) employees executing the unblinding receive access to the randomization codes and unblinded data for the purpose of preparing the interim analyses. Interim analyses are only intended to determine if the trial has met criteria for efficacy. Further details regarding the interim analysis are described in the DMC Charter and in Appendix C.

Primary Efficacy Analysis:

Nasopharyngeal swab samples in this study will be analyzed in batches and the number of RT-PCR confirmed influenza cases and its antigenic match to the influenza vaccine strain will be reviewed on a regular basis (blinded review) throughout the study.

An interim analysis for efficacy may be performed, if deemed necessary by the Sponsor:

- If the number of RT-PCR confirmed influenza cases is less or equal to 95 overall, no interim analysis for efficacy will be done and the study will be extended because the probability to make a conclusion for efficacy is too low.
- If the number of RT-PCR confirmed influenza cases is greater or equal to 96 but less than 191, an unblinded interim analysis for efficacy may be performed. To maintain the overall alpha, $\alpha = 1.25\%$ (1-sided), for the hypotheses testing for the primary objectives, an error-spending-function will be used. The benefit of using an error-spending-function is that no maximum number of analysis stages and the timing of the analyses need to be pre-specified, what in practice

Statistical Analysis Plan – Final v2.0

Sponsor Name: Seqirus UK Limited
Sponsor Protocol ID: V130_14

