means that the duration of the study in terms of number of seasons can be left open. In this case α -boundaries, forming the adjusted probabilities for the type I error, are calculated using error-spending function and if the p-value for one primary objective is lower than the respective α -boundary the trial stops early (i.e., without reaching the targeted number of cases of 191) for efficacy. Otherwise, the trial continues enrollment. Decisions to stop or continue the trial will be made based on discussions between the DMC and Senior Management.

- If the number of RT-PCR confirmed influenza cases is greater or equal to 191, the study may be unblinded and the final analysis may be performed by the Sponsor. If the trial proceeds to the final analysis (upon reaching 191 cases) the boundaries for acceptance or rejection are identical to the assumed type I and type II errors for the overall design, and the trial stops to either reject or accept the null hypothesis of either one or / and the other of the primary objectives.

In case the DMC states that the observed data provides already the full information level needed for the final test decision, then the final analysis can be done on full alpha level and no further enrollment is needed. However, if the decision of the group-sequential test is to continue the study then it is on the DMC to determine the number of subjects needed to be enrolled. The monitoring committee should not be influenced by the individual results of the study vaccine groups observed at an interim analysis stage when planning further subjects' accrual or the times of future analysis. Only the overall number of cases is allowed to be used for further planning.

The following formula for determination of sample sizes for further enrollment may be used:

$$N_{\text{total}} = (C_{\text{planned}} - C_{\text{observed}}) / [(ER_{QIVc} + ER_{comp})/2],$$

where N_{total} denotes the total number of subjects needed for further enrollment, C_{planned} is the overall number of cases needed for the test, i.e 191 cases, C_{observed} are the at that stage observed number of cases overall, and ER are the respective attack rates assumed for each group. A consideration of early dropout and uncertainty about assumed parameters will be accounted for number of enrolled subjects.

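### The 191-case clause in protocol 8.6 and SAP 6.8 lets endpoint 1b be tested with no matched-case condition and says the design type II error holds there; at the plan's rates 1b power at exactly 191 RT-PCR cases is 85%, not 90%

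*SAP*

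**What the plan says.** **The clause.** Protocol 8.6: "If the number of RT-PCR confirmed influenza cases is greater or equal to 191, the study may be unblinded". SAP 6.8 has the same bullet: if the RT-PCR case count is "greater or equal to 191, the study may be unblinded and the final analysis may be performed by the Sponsor". Both add that at the final analysis "the boundaries for acceptance or rejection are identical to the assumed type I and type II errors for the overall design", and that the trial then stops with a decision on one or both primary objectives. Neither bullet mentions a matched-case count.

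**The design.** For 1b, SAP 2.3 says that "a minimum number of 104 cases are needed to have at least 90% power". It adds: "The study is designed to accrue a minimum of 191 RT-PCR confirmed influenza cases and a minimum of 104 culture confirmed influenza cases". Protocol 3.1 asks for "both a minimum of 191 RT-PCR confirmed influenza cases and a minimum of 104 culture confirmed influenza cases"; the synopsis and protocol 8.5 also give the two minima. These passages describe what the study is designed to accrue, and they allow the counts to be adjusted. They do not say when the final analysis is triggered.

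**Appendix C of the SAP.** After an unsuccessful first interim, the study continues to 191 RT-PCR and 104 matched cases unless a second interim is recommended. A sponsor who skips the second interim goes to the final analysis when both counts are reached. A second interim may be held at 52 or more matched cases; if there are then at least 300 RT-PCR cases, 1a receives its final analysis.

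**Links between them.** SAP 6.8 says: "Further details regarding the interim analysis are described in the DMC Charter and in Appendix C". In the re-enrolment formula, C_planned "is the overall number of cases needed for the test, i.e 191 cases". The information fraction in SAP 6.8 uses the same symbol and gives no separate value for 1b.

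**The concern.** Power for 1b depends on the number of matched cases, and the clause counts only RT-PCR cases. A statement that the design type II error applies at 191 RT-PCR cases can hold for 1b only if those cases bring about 104 matched cases with them. The plan's attack rates imply fewer. If the sponsor used the permission as soon as it opened, a primary endpoint would be tested with less power than the plan states, and unblinding cannot be undone. The re-enrolment formula has the same gap, because it aims at 191 RT-PCR cases and ignores the matched count.

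**Working it through.** **Inputs** (SAP 2.3 and 6.8): one-sided alpha 0.0125 per endpoint (z = 2.2414); 1:1 allocation; 1a comparator attack rate 8%, VE 40% (HR 0.6); 1b comparator attack rate 4%, VE 50% (HR 0.5); power at least 90%.

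**1. Reproduce the plan's counts.** Schoenfeld's formula, 1:1: d = 4(z_alpha + z_beta)² / (ln HR)².
- 1a: 190.3, rounded up to 191; power at 191 is 90.1%.
- 1b: 103.3, rounded up to 104; power at 104 is 90.2%.

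Both match the documents.

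**2. Matched cases expected at 191 RT-PCR cases.**
- Pooled RT-PCR rate: (0.08 + 0.048)/2 = 0.064.
- Pooled matched rate: (0.04 + 0.02)/2 = 0.030.
- Implied matched share: 0.030/0.064 = 46.9%. The documents do not state this ratio; it follows from their rates.
- Evaluable subjects when 191 cases are expected: 191/0.064 = 2,984.
- Matched cases then expected: 2,984 × 0.030 = 89.5.

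**3. Power for 1b.** Power = Φ(ln 2 × √d / 2 − 2.2414). At d = 89.5 this is 85.0%, a type II error of 15.0%. Deriving the QIVc rates under proportional hazards instead gives 89.3 cases and 84.9%.

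**4. Other matched shares.** Appendix C itself notes that the matched proportion varies by season. The shares below, other than 46.9%, are assumptions.

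| Matched share | Matched cases at 191 RT-PCR | Power for 1b |
|---|---|---|
| 30% | 57.3 | 65% |
| 40% | 76.4 | 78% |
| 46.9% (plan) | 89.5 | 85% |
| 50% | 95.5 | 87% |
| 60% | 114.6 | 93% |

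Break-even is 104/191 = 54.5%. Above that share there is no loss.

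**5. If the planned size is reached.** With 3,446 evaluable subjects: 3,446 × 0.064 = 220.5 RT-PCR cases, 3,446 × 0.030 = 103.4 matched cases, and power for 1b of about 90%. The shortfall therefore needs a stop about 3,446 − 2,984 = 462 evaluable subjects short of plan.

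**6. Re-enrolment formula.** Take an interim at 96 RT-PCR cases with 96 × 0.469 = 45 matched. Before any allowance for dropout or parameter uncertainty, the formula gives (191 − 96)/0.064 = 1,484 further evaluable subjects and a final matched count of 45 + 1,484 × 0.030 = 89.5. Reaching 104 needs (104 − 45)/0.030 = 1,967.

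**The case against.** The strongest reply is that the dual count is already the plan. The clause says *may*, the two minima appear in several places, and enrolment is sized on 1b, so a sponsor following the plan would hold about 103 matched cases. Waiting for both counts complies with every passage. This stands, and it makes 85% the value at exactly 191 cases rather than the expected result. It does not rescue the type II sentence, which is tied to reaching 191 RT-PCR cases and is untrue for 1b at that point.

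A second reply is that a reader might infer a flat contradiction between SAP 6.8 and Appendix C on every path. The text does not support that. Appendix C's dual count is written for the path after an unsuccessful first interim, so the 191-case bullet can be read as the path with no interim. On that path the tension is only with the design minima. The conflict is direct after an unsuccessful first interim. The decision-tree flowchart is not shown in the text reviewed, and the DMC Charter is not part of it. Either might settle the order of precedence, so the claim is limited to the visible text.

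Third, the formula and information-fraction points are small. The formula is optional and allows for dropout and uncertainty. Appendix C's Table 1 gives 52 cases as half the required matched count, which implies 104. Both are fair, but 104 should still be stated where the symbol is defined.

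**Conclusion.** The concern holds in a limited form. The clause permits, but does not require, the final test of 1b at 191 RT-PCR cases, and its type II statement is wrong for 1b at the plan's rates: about 15% at exactly 191 cases, against at most 10% in the design. The loss arises only if the permission is used early and the matched share is below 54.5%. The size rests on the planned attack rates, a constant hazard ratio and the 1b VE of 50%.

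A reader might also infer that the trial as a whole is underpowered or that type I error is inflated. Neither follows. Success needs only one endpoint and 1a has 90.1% power at 191 cases, so power for the primary objective is at least that. Nothing in this point affects alpha. The severity is minor to moderate.

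**What to change.** In protocol 8.6 and SAP 6.8:

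1. Reword the bullet so that, unless the study stops for efficacy at an interim or Appendix C's second-interim rules apply, the final analysis *may* be performed once at least 191 RT-PCR and at least 104 matched cases (or the counts as adjusted under SAP 2.3) have accrued.
2. State that the Appendix C release (a look at 52 or more matched cases, with the final 1a analysis at 300 or more RT-PCR cases) is also available when no first interim was held in the 96 to 190 window. Appendix C now describes it only after a first interim, so passing 191 without one would leave no release.
3. State C_planned as 191 for 1a and 104 for 1b. Where the re-enrolment formula is used, apply it to each endpoint with pooled counts only and take the larger result: max[(191 − C_RT)/0.064, (104 − C_matched)/0.030] at the assumed rates.

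Alternatively, keep the 191-only permission, limit the type II statement to 1a, and give 1b power as about 85% at exactly 191 RT-PCR cases under the planning rates.

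**Cost.** A SAP revision and a protocol amendment with the approvals in protocol 13.4. At planning rates the dual count needs 104/0.030 = 3,467 evaluable subjects against 3,446 planned. A lower matched share lengthens the trial, as Appendix C already implies: at assumed shares of 40% and 30%, 104 matched cases need 260 and 347 RT-PCR cases, or about 4,060 and 5,420 evaluable subjects. The release itself needs 52 matched cases, which at 300 RT-PCR cases is a share of 17.3% (52/300).

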Additional interim analyses may be requested at a future date (by the DMC), particularly if the first interim analysis is conducted soon after 96 cases of influenza have been reported. In this case, the DMC may request that a second interim analysis be conducted to allow for greater accuracy to determine if the trial should stop or continue.

Table 6 shows the needed total number of cases at each stage of the two-stage design together with boundaries for early stopping efficacy, calculated on p-value scale using the cumulative error spending function. With half the information collected at the stage of interim analysis (that is, with exactly 96 confirmed ILIs) the

Statistical Analysis Plan – Final v2.0

Sponsor Name: Seqirus UK Limited

Sponsor Protocol ID: V130_14

trial would stop early for efficacy if the p-value is lower than 0.0004120. Otherwise the trial will be continued, and more subjects will be enrolled. The actual boundaries used for decision making would depend on number of confirmed ILIs occurring and reported for Interim Analysis.

Table 6: Example of a Two Stages Group-Sequential Design

	Stage 1	Stage 2
	First	Final
Number of Events	96	192
Alpha Boundary on p-value scale (equivalent to Type 1 error, 1-sided), early stopping for efficacy	0.0004120	0.01236

The stopping rules are statistically determined and should be complemented by clinical and strategic stopping rules that allow the DMC to make a decision on a broader picture of the data. Another interim look at the data with appropriate adjustment of type 1 error might be recommended before reaching the targeted 191 cases.

The comparison of the test statistic with its boundary values will be performed by using the SAS® SEQTEST procedure. The boundary information tables calculated by PROC SEQDESIGN

(<https://support.sas.com/documentation/onlinedoc/stat/131/seqdesign.pdf>) at an analysis stage are structured for input to the SEQTEST procedure. At each subsequent stage, the boundary values are derived by using the test information tables created by the SEQTEST procedure at the previous stage. These test information tables are also structured for input to the SEQTEST procedure. PROC SEQTEST can also be used to compute parameter estimates, confidence limits, and p-values after the trial stops.

For the interim analyses, a restricted unblinding will be done, i.e., only DMC members and unblinded CRO employees responsible for the analyses will receive access to the randomization codes and unblinded data for the purpose of preparing the interim analyses (further information on handling of the blinding for the interim analyses can be found in protocol section 3.3). The results of the interim analyses are only for DMC purposes and will not be reported in the CSR.

7 Changes in Planned Analysis

The term 'sex' has been replaced with 'gender' throughout the analysis section. The definition of FAS Overall has been added to this SAP for baseline and background data description purpose.

8 Data Issues

Not applicable.

9 References

- 1 ICH. *Statistical Principles for Clinical Trials*, Guideline E9, 1998. Available at <http://www.emea.eu.int/pdfs/human/ich/036396en.pdf>
- 2 CPMP. *Points to Consider on Missing Data*. EMEA: London, 2001. Available at <http://www.emea.eu.int/pdfs/human/ewp/177699EN.pdf>
- 3 Phillips A and Haudiquet V. *ICH E9 guideline "Statistical principles for clinical trials": a case study*. Statistics in Medicine 2003; 22:1-11
- 4 Brown D J. *ICH E9 guideline "Statistical principles for clinical trials": a case study. Response to A. Phillips and V. Haudiquet*. Statistics in Medicine 2003; 22:13-17
- 6 Senn S. *Statistical Issues in Drug Development*. John Wiley & sons (Chichester), 1997.
- 7 Chow S-C and Liu J-P. *Design and Analysis of Clinical Trials: Concepts and Methodologies*. John Wiley & sons (New York), 1998.
- 8 Brown H and Prescott R. *Applied Mixed Models in Medicine*. John Wiley & sons (Chichester), 1999.
- 9 Fairclough D L. *Design and Analysis of Quality of Life Studies in Clinical Trials*. Chapman & Hall/CRC, 2002.
- 10 Green S, Benedetti J and Crowley J. *Clinical Trials in Oncology (2nd edition)*. Chapman & Hall/CRC, 2002.
- 11 McEntegart D. *Forced randomization when using interactive voice response systems*. Applied Clinical Trials October 2003; 50-58.
- 12 CPMP. *Points to Consider on Adjustment for Baseline Covariates*. EMEA: London, 2003
